1. ABBREVIATIONS

ANSM: French National Agency for Medicines and Health Products Safety ARC:

Clinical Research Associate

Stroke: Cerebrovascular Accident

GCP: Good Clinical Practice MHC:

Medical-Surgical Center

CNIL: National Commission for Information Technology and Civil

Liberties CPP: Committee for the Protection of Persons

CRF: Standardized Data Collection Form

ICD: Implantable Cardioverter Defibrillator AF:

Atrial Fibrillation

MR: Reference Methodology

GDPR: General Data Protection Regulation RICAP:

Research and Innovation at the Ambroise Paré Medical-

Surgical Center TD: Defibrillation Test

2. SCIENTIFIC JUSTIFICATION AND GENERAL DESCRIPTION OF THE RESEARCH

2.1. Study Context

Over the years, advances in technology and knowledge, as well as evolving clinical practices, have led to the routine discontinuation of the defibrillation test (DT) during the implantation of an implantable cardioverter-defibrillator (ICD). Furthermore, improved monitoring through telemetry has enhanced patient safety by enabling the early detection of chronic lead malfunctions.

While this approach is logical during the initial implantation of a defibrillator and has been demonstrated by numerous studies, the question of whether to perform this test during device replacement remains open. Indeed, the leads are older at that point, potentially more fragile, and handling the connectors exposes them to an increased risk of wear ¹.

The defibrillation lead remains the weak link in a defibrillation system: its design is complex, and it is subjected to constant mechanical stress from the surrounding tissues. The overall operational rate of a defibrillation lead is 89% at 5 years, but this rate decreases ² rapidly thereafter, reaching 60% at 8 years ^{2,3}. Certain general characteristics (female gender, young patient) and the venous access route (subclavian) appear to increase the risk of lead wear.

When replacing the housing, handling the lead—which involves using an electrosurgical knife in close proximity to dissect the tissue and expose the connectors encased in fibrosis, as well as applying gentle traction to release the lead from the connector and reconnect it—requires meticulous technique ⁴, especially since older leads are more fragile ⁵. Some studies have reported a dysfunction rate of 3.5% one year after the housing replacement ⁶. Furthermore, the occurrence of technological failures in certain catheters (Fidelis, Riata) necessitated increased monitoring of these devices, which provided a better understanding of the impact of the hush on failures. Thus, it has been reported that these failures occurred at rates comparable to those of “control” leads without recall ⁷, but more rapidly over time. For the Fidelis lead, there also appears to be a peak within 3 months after lead system replacement ⁸.

In light of these findings, the TD during housing changes requires further study before it can be discontinued. This is the aim of this study.

2.2. Research Objective

The objective of this study is to demonstrate that the TD during defibrillator enclosure replacement enables the early detection of potential defibrillation circuit failures.

2.3. Summary of the benefits, if any, and the foreseeable and known risks for research participants

2.3.1. Expected benefits for the patient

Testing the defibrillation circuit, by enabling early detection of potential lead abnormalities, would lead to their replacement, thereby reducing the risk of inappropriate shocks and failure to treat serious arrhythmias.

2.3.2. Foreseeable and known risks

The risks associated with a defibrillation test are low. However, they must be weighed against the expected benefits. The largest registries suggest that the risk of major complications, including stroke, pulmonary embolism, cardiogenic shock, or

hypotension requiring resuscitation, have an estimated incidence of 0.17–0.4%, and that the risk of mortality is estimated at 0.016–0.07%^{9,10}.

A recent update of data on defibrillation testing suggests that this practice is no longer warranted during the initial implantation of a defibrillator, but should be reserved for specific cases and certain patient populations¹¹.

For all the reasons outlined in the scientific rationale for our protocol, we believe that defibrillator replacement procedures fall into this category of specific cases, due to the potential fragility of the older lead compared to that encountered during initial implantation.

Furthermore, the data above pertain to the defibrillation test involving the induction of ventricular fibrillation, as was conventionally performed in the past, whereas in our study we propose prioritizing a QRS-synchronized shock, which has the advantage of not disrupting the patient's hemodynamics. Finally, we chose to exclude patients at high risk of undergoing this test. These various reasons allow us to avoid the complications described above.

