5.2. Exclusion criteria

Patients meeting the following criteria will not be included:

- Atrial fibrillation (AF) without effective anticoagulation for a shock,
- Severe aortic stenosis,
- Stroke occurring within the month prior to enrollment,
- Hemodynamic instability contraindicating shock therapy,
- Contraindication to anesthesia,
- Pregnant or breastfeeding women,
- Inability to understand the information provided,
- Under guardianship, conservatorship, or judicial protection.

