6.2.2. In the operating room

The procedure will be performed under general anesthesia or sedation, at the physician's discretion.

a) Before replacing the defibrillator's housing

Testing the lead parameters on the old defibrillator case

b) Replacement of the defibrillator housing

Replacement of the defibrillator housing and visual inspection of the connectors, following standard procedure.

After replacing the defibrillator housing

- Testing of probe parameters before and after connection to the new housing.
- Testing the defibrillation circuit:

Either via the standard defibrillation test, which involves inducing a ventricular arrhythmia through electrical cardiac stimulation and verifying the quality of its detection and the effectiveness of defibrillation.

Or via a high-energy synchronized shock; the test involves delivering a high-energy electrical shock synchronized with the QRS complex, in accordance with each manufacturer's standard guidelines (Appendix 1).

Important points:

- The use of an electrosurgical unit during surgery must be specified by the investigator, as its use may increase the risk of damaging the probe.
- If a malfunction of the defibrillation lead is detected during surgery, it will be replaced during the same procedure.

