16. APPENDICES

Appendix 1: Defibrillation circuit testing using synchronized high-energy shocks by manufacturer.

APPENDIX 1: TEST OF THE SYNCHRONOUS HIGH-ENERGY SHOCK DEFIBRILLATION CIRCUIT BY MANUFACTURER.

AED	Defibrillation Circuit Test	Expected impedance value
MEDTRONIC	Delivery of a synchronized shock to a spontaneous QRS (cardioversion) at a maximum energy of 35 J. In the event of a circuit break, the ICD will protect itself and will not deliver a shock. In the case of a pacemaker-dependent patient, the ICD cannot perform cardioversion (no synchronization possible on a Vs), it must then choose a defibrillation at 35J.	< 150 Ω
SJM/ABBOTT	Delivery of a synchronized shock on a spontaneous QRS with a recommended energy of 36 J. Retrieval of the shock impedance by re-querying the defibrillator.	20–120 Ω
BIOTRONIK	Delivery of a manual R-wave shock at 40 J.	50–150 Ω
BOSTON SCIENTIFIC	Delivery of two synchronized shocks triggered by the R-wave. A first shock at 1.1 J, followed by a ^{second} verification shock at 41 J. Only the combination of these two tests can truly confirm the integrity of the system, particularly the leads.	15 – 120 Ω
MICROPORT	Delivery of a 42 J shock (maximum energy) Program therapies in advance, which allows the ICD, in the event of arrhythmia induction, to diagnose and treat the triggered arrhythmia.	30–60 Ω (dual-coil probe) 50–10 Ω (single-coil probe)

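### Section 2.3.2 relies on giving priority to a synchronized shock, but section 6.2.2 leaves the two tests unranked and no section asks which test was delivered

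*Combined protocol and SAP*

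**What the plan says.** Section 2.3.2 gives the registry risks (0.17–0.4% major complications, 0.016–0.07% mortality) and says that they come from tests that induce ventricular fibrillation. It sets this study apart on two grounds. The first is a choice of technique: "in our study we propose prioritizing a QRS-synchronized shock". The second is the exclusion of patients at high risk from the test. It then concludes: "These various reasons allow us to avoid the complications described above".

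Section 5.2 acts on the second ground, for example with "Hemodynamic instability contraindicating shock therapy".

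Section 6.2.2, which the operator follows, gives two routes for the circuit test: "Either via the standard defibrillation test, which involves inducing a ventricular arrhythmia through electrical cardiac stimulation", or the second option, "Or via a high-energy synchronized shock", for which it refers to Appendix 1. The schedule in section 6.3 has a single row for the circuit test and marks it as added by the research.

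Section 12.5 lists the result of the circuit test, the ICD impedance and any complications among the intraoperative data. It does not list which test was used. Section 12.1 says that whatever the protocol requires goes into the eCRF.

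**The concern.** The circuit test is added by the research, so its risk is imposed by the study, and section 2.3.2 itself says that this risk must be weighed against the benefit. One of the two measures said to limit it is stated in the rationale but is not turned into an instruction. A site that follows section 6.2.2 has no default test and no criterion for when induction is acceptable.

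The test delivered is not a specified data item either. Section 8.1 would give overall frequencies and percentages, with no breakdown by test. Section 7 sends adverse events to routine vigilance without a specific study report. If a major complication occurs, the study dataset may not show whether it followed an induced or a synchronized test, and the sponsor may be unable to report how far its stated preference was followed.

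**Working it through.** **1. Is each safeguard carried out?**

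| Safeguard in 2.3.2 | Where it should take effect | What is there |
|---|---|---|
| Exclude high-risk patients | 5.2 | Carried out: AF without effective anticoagulation, severe aortic stenosis, recent stroke, instability, contraindication to anesthesia |
| Give priority to the synchronized shock | 6.2.2 | Two alternatives, induced test listed first; no order, default or criterion. The only discretion mentioned is between general anesthesia and sedation |
| Show which test was used | 6.3, 12.5, 8.1 | One row for the circuit test; a result and an impedance; no test type; no analysis by test |

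Section 12.1 does not close the last gap, because it covers only what the protocol requires and no section requires the test type. Electrosurgery is a useful contrast. It too is absent from 12.5, but 6.2.2 does ask for it: "The use of an electrosurgical unit during surgery must be specified by the investigator". So 12.1 picks it up. The same holds for postoperative complications, which 6.2.3 and 6.3 require.

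**2. Does any endpoint need induction?** The primary endpoint (4.1) is an abnormal shock impedance judged against Appendix 1. The M3 and M12 endpoint (4.2) is based on impedance, and the remaining one relates malfunction to lead type and clinical variables. Induction also checks detection and defibrillation efficacy, but no endpoint uses either.

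**3. Size, from the protocol's own rates.** Inputs: major complications 0.17–0.4% and deaths 0.016–0.07% (2.3.2); N = 330 (8.2). The sample-size figure reproduces: 0.99^299 = 0.0495, below 5%, while 0.99^298 = 0.05004. So 299 is the smallest n, raised to 330 for unusable data and withdrawals.

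For m induced patients at rate p, the expected count is m × p and P(at least one) = 1 − (1 − p)^m. With all 330 induced:

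- Major complications: 330 × 0.0017 = 0.561 and 330 × 0.004 = 1.32. P(at least one) = 1 − 0.9983^330 = 0.430 and 1 − 0.996^330 = 0.734.
- Deaths: 330 × 0.00016 = 0.053 and 330 × 0.0007 = 0.231. P(at least one) = 1 − 0.99984^330 = 0.051 and 1 − 0.9993^330 = 0.206.

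If only 299 were tested, all by induction, the expected major complications would be 0.51–1.20.

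The induced share is not in the documents. The shares below are assumptions:

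| Assumed share | Patients | Major complications expected | P(at least one) | Deaths expected |
|---|---|---|---|---|
| 10% | 33 | 0.06–0.13 | 5–12% | 0.005–0.023 |
| 25% | 82 | 0.14–0.33 | 13–28% | 0.013–0.057 |
| 50% | 165 | 0.28–0.66 | 24–48% | 0.026–0.116 |

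No figure allows for the 5.2 exclusions. The documents give no rate for a synchronized shock, or for a non-synchronized shock without induction.

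**The case against.** The strongest reply is that the preference is already in the protocol. Section 2.3.2 states it for this study, section 6.2.2 refers to Appendix 1 for the synchronized route, Appendix 1 gives manufacturer instructions for that route only, and the primary endpoint rests on the same appendix. A reasonable investigator would infer what is wanted. This stands as far as it goes: the intention is clear. It does not tell the operator when induction is acceptable, and 6.2.2 treats the tests as equals.

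Four stronger readings are tempting, and the documents do not support them.

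- *Adherence to the priority cannot be checked at all.* Section 10.1 has monitoring visits review compliance with the protocol and agreement with source documents, and the circuit test result may itself reveal the test. The eCRF is not among the documents. What can be said is that the test type is not a specified data item.
- *The trial carries a 43–73% chance of a major complication.* That needs every patient to be induced, against the stated intention, and ignores the exclusions.
- *Appendix 1 shows that the quoted complications will occur.* For pacemaker-dependent Medtronic patients it specifies a 35 J defibrillation and does not mention induction. The Microport advice to program therapies, "in the event of arrhythmia induction, to diagnose and treat the triggered arrhythmia", is a precaution and says nothing about rates.
- *Postoperative complications and electrosurgery go unrecorded.* Sections 6.2.2, 6.2.3, 6.3 and 12.1 cover them; their absence from 12.5 is only an inconsistency in a short list.

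It is also fair to say that complications are not an endpoint and that counts by test will be too few to compare. That argues for descriptive reporting only, and against making an interval estimate a requirement.

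**Conclusion.** The point holds in a limited form. The priority on which section 2.3.2 partly rests its risk argument is not an operative instruction, and no section asks for the test delivered, so complications may not be attributable to test type. The claim that complications are avoided is too strong because induction remains permitted in any included patient; a claim that they are reduced could be supported.

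The expected 0.56–1.32 major complications and 0.05–0.23 deaths are upper bounds for 330 induced patients at the cited rates. They are not a forecast. The likely figure depends on an induced share that the documents do not give and on the unquantified effect of the exclusions. The case for change rests on the mismatch between 2.3.2 and 6.2.2 for a research-added procedure, and on how little it costs to correct. It does not rest on the size of the upper bound.

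**What to change.** - **Section 6.2.2.** State that the synchronized shock per Appendix 1 is first choice. The induced test, or the Appendix 1 35 J defibrillation in pacemaker-dependent Medtronic patients, is used only when a synchronized shock cannot be delivered or for a recorded clinical reason.
- **Section 2.3.2.** Say that the measures are expected to reduce the complications. Add that patients who have an induced test remain exposed to the risks of induction, with the cited registry rates as a reference before exclusions.
- **Section 12.5.** Add the test or tests attempted and delivered (synchronized / induced / non-synchronized without induction / none), with more than one allowed so that a failed synchronized attempt followed by another test can be recorded. Add whether an arrhythmia was triggered, and the reason for any induced or non-synchronized test.
- **Section 8.1.** Report complication counts by test delivered, descriptively. An exact confidence interval for the overall rate is optional.

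The cost is some wording, a few eCRF items and one descriptive table, with no extra patients. Physicians must give a reason for choosing induction, and the risk statement becomes less favourable. The primary endpoint, its analysis and the sample size do not change.

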2.4. Description of the study population

Adult patients scheduled for an ICD lead replacement.

3. RESEARCH OBJECTIVES

3.1. Primary objective

The primary objective of the study is to demonstrate a non-zero failure rate of the defibrillation circuit during a device replacement.

3.2. Secondary Objectives

The secondary objectives are to:

1. Determine the failure rates of defibrillation leads 3 and 12 months after the implantable device replacement.
2. Identify clinical variables that may be associated with a risk of failure.
3. Identify potential catheters at risk of failure.

4. EVALUATION CRITERIA

4.1. Primary endpoint

The primary endpoint is the intraoperative catheter failure rate based on an abnormal shock impedance value (as defined by the manufacturer in Appendix 1).

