4.2. Secondary endpoints

In relation to secondary objective 1:

Probe malfunction rate at the follow-up visit at M3 and M12 based on an abnormal impedance value (stimulation circuit and shock impedance) recorded during probe parameter testing.

In relation to secondary objectives 2 and 3:

Correlation between the probe malfunction rate and probe type and patient clinical variables.

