6.2.4. Follow-up at 3 months and 1 year post-procedure

A standard follow-up visit to check the defibrillator is scheduled 3 months (\pm 3 months) and 12 months (\pm 3 months) after the procedure. This follow-up involves testing the lead's standard parameters (sensitivity, pacing threshold, pacing impedance, and defibrillation impedance), as well as downloading the device's memory to ensure there have been no abnormal signals from the lead since the procedure.

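### The single overall rate of abnormal shock impedance does not isolate failures found only by the circuit test, so it cannot by itself support the early-detection aim of section 2.2

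*Combined protocol and SAP*

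**What the plan says.** Section 2.2 sets the overall aim: to "demonstrate that the TD during defibrillator enclosure replacement enables the early detection of potential defibrillation circuit failures". Section 3.1 turns this into a narrower formal objective, to "demonstrate a non-zero failure rate of the defibrillation circuit during a device replacement". The endpoint in section 4.1 follows the narrower one: "The primary endpoint is the intraoperative catheter failure rate based on an abnormal shock impedance value", with limits by manufacturer in Appendix 1. Section 8.1 plans a point estimate and 95% confidence interval for the dysfunction rate, and section 8.2 sizes the trial on the total malfunction rate.

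The circuit test is not the only intraoperative check. Section 6.2.2 lists ahead of it "Testing the lead parameters on the old defibrillator case", a visual inspection of the connectors, and "Testing of probe parameters before and after connection to the new housing". The design table in section 6.3 marks the old-case test R (added by the research), and the inspection and the tests around connection S (care).

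Section 6.2.2 does not itemise the intraoperative parameters. At follow-up, section 6.2.4 includes "pacing impedance, and defibrillation impedance" among the lead's standard parameters, and section 4.2 defines malfunction as "based on an abnormal impedance value (stimulation circuit and shock impedance) recorded during probe parameter testing".

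**The concern.** To show that a test enables early detection, one needs to know what it finds that the checks already made did not. If parameter testing can return shock impedance, some leads that meet the endpoint may have been visibly abnormal before the circuit test. The planned analysis pools them with leads that only the circuit test revealed.

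Two very different results would then be reported identically: one in which the circuit test found every failure, and one in which it confirmed faults already on record. Section 2.3.2 says that the test's risks must be weighed against its expected benefits. The additional yield is the quantity that belongs in that weighing, and no planned analysis produces it.

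**Working it through.** **Inputs**
- Total malfunction rate 1%, 299 evaluable patients, 330 enrolled, 5% threshold: section 8.2.
- Share f of counted failures that only the circuit test reveals: not in the documents. Assumed here, from 100% down to 0%.
- Counting rule: every abnormal shock impedance counts, whether or not the lead was already found abnormal. This is also an assumption, because the documents do not state it.

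**Step 1: the plan's own figure.** The smallest n with 0.99^n < 0.05 is ln(0.05)/ln(0.99), rounded up, which is 299. Check: 0.99^298 = 0.05004 and 0.99^299 = 0.04954. The allowance up to 330 is 31/330 = 9.4%. The stated sample size is reproduced.

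**Step 2: what that figure covers.** P(at least one counted failure) = 1 − 0.04954 = 0.95046, or 95.0%. The share f does not enter, so the figure is 95.0% even at f = 0.

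**Step 3: failures found by the circuit test alone.** Their rate is 0.01 × f.
- P(none) = (1 − 0.01f)^299.
- P(at least one failure counted, none of them circuit-test-only) = P(none) − 0.04954.
- Evaluable n for P(none) < 5% is ln(0.05)/ln(1 − 0.01f), rounded up.

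| f (assumed) | Rate | P(none) in 299 | P(at least one) | P(failure counted, none circuit-test-only) | n for P(none) < 5% |
|---|---|---|---|---|---|
| 100% | 1.00% | 0.0495 | 95.0% | 0% | 299 |
| 75% | 0.75% | 0.1053 | 89.5% | 5.6% | 398 |
| 50% | 0.50% | 0.2234 | 77.7% | 17.4% | 598 |
| 25% | 0.25% | 0.4731 | 52.7% | 42.4% | 1197 |
| 0% | 0% | 1 | 0% | 95.0% | none |

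**Step 4: an illustration.** Three failures in 299 give 1.0%, with an exact 95% interval of 0.21% to 2.90%, which excludes zero. If all three had been visible on earlier testing, the circuit-test-only yield would be 0/299, with an exact 95% interval of 0% to 1.23%. The section 8.1 analysis reports the first line and not the second.

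**The case against.** The strongest reply is that the endpoint, analysis and sample size all match the formal primary objective in section 3.1, which asks only for a non-zero circuit failure rate. This stands: the primary estimate is valid for that objective, and section 2.2 does not itself say that detection must go beyond parameter testing. The gap lies between the formal objective and the broader aim.

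The overlap may also be small. Patients enter for battery wear (section 5.1), and section 2.1 credits telemetry with early detection of chronic lead faults, so few enrolled leads may have a known defect. That is plausible but not assured, since sections 5.1 and 5.2 do not exclude leads already abnormal. If intraoperative parameter testing does not return shock impedance, the overlap shrinks further; its inclusion is an inference from sections 4.2 and 6.2.4.

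A reader might draw several stronger conclusions that the documents do not support:
- That every abnormal lead is counted. Only abnormal shock impedance is; a lead abnormal solely on pacing impedance, sensing, threshold or inspection is not.
- That a lead abnormal on the old case is credited to the circuit test by rule. Section 6.2.2 provides for replacing a malfunctioning lead in the same procedure, but no section says how one found abnormal earlier is counted.
- That all the earlier checks are ordinary care. The old-case test is marked R.
- That anaesthesia or sedation is a burden of the shock test. Section 6.2.2 attaches it to the procedure as a whole.

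**Conclusion.** The point holds in a limited form. The primary result can establish a non-zero rate of abnormal shock impedance. It cannot by itself establish that "the TD during defibrillator enclosure replacement enables the early detection of potential defibrillation circuit failures", because failures found only by the circuit test are not separated from those already shown.

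At a 1% total rate and 299 evaluable patients, the 95.0% chance of at least one counted failure is unaffected by what the circuit test adds. The chance of at least one circuit-test-only failure is 89.5%, 77.7% or 52.7% for assumed shares of 75%, 50% or 25%. These sizes depend on assumed shares, on the inference that intraoperative parameter testing includes shock impedance, and on leads found abnormal earlier being counted. It would be too strong to call the primary endpoint wrong or the sample size miscalculated: both serve section 3.1. What is missing is an inexpensive analysis that would let the trial address section 2.2.

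**What to change.** Keep the total rate as the primary endpoint and keep the sample size. In the analysis plan:

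1. State how a lead found abnormal before the circuit test is counted in the primary endpoint, and list which intraoperative parameters are recorded.
2. Add a pre-specified key secondary analysis that cross-tabulates the circuit-test result against the preceding checks. Classify failures as (a) abnormal on the old case, (b) newly abnormal on parameter testing or inspection after the exchange, or (c) abnormal on the circuit test only. Report each rate with an exact 95% confidence interval.
3. State that the section 2.2 conclusion rests on category (c), and that 299 was chosen for the total rate and not for this one.

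No additional patients or procedures are needed. The cost is wording in the analysis plan and possibly a few eCRF fields: section 12.5 lists a single intraoperative parameter-test result and no inspection finding, so results by time point and the inspection outcome may have to be added. The downside is that the circuit-test-only rate cannot exceed the total rate, will probably be lower, and may rest on very few events or none.
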